### Study design and participants

This prospective, randomized, and controlled study was conducted between June 2021 and June 2022 at the Department of Physical Medicine and Rehabilitation (PMR), University Hospital. Patients diagnosed with FM according to the 2016 ACR diagnostic criteria were evaluated for eligibility. In accordance with the ACR diagnostic criteria, three conditions are required to be met: 1) The presence of symptoms of similar severity for at least 3 months; 2) A widespread pain index (WPI)  $\geq 7$  and a symptom severity scale (SSS) score  $\geq 5$ , or a WPI of 4–6 and an SSS score  $\geq 9$ ; 3) Generalized pain in at least 4 out of 5 regions [7]. The inclusion criteria were as follows: age between 18 and 65 years; voluntary participation in the study; diagnosis of fibromyalgia according to the 2016 ACR criteria; female gender; and a pain severity score of  $\geq 4/10$  on the Visual Analog Scale (VAS). The exclusion criteria included pregnancy, a history of malignancy, pre-existing neurological, endocrine, infectious, or inflammatory rheumatic diseases, severe psychiatric disorders, advanced cardiac, respiratory, or musculoskeletal conditions that would prevent exercise, participation in an exercise or physical therapy program within the last 6 months, and any changes to current medical treatment during the study period. A written informed consent was obtained from each patient. The study protocol was approved by the Interventional Research Ethics Committee (Date: 31/05/2021, Number: 2021/02). The study was conducted in accordance with the principles of the Declaration of Helsinki.

A total of 60 female patients (mean age:  $48.0 \pm 9.7$  years; age range: 28 to 65 years) participated in the study. The patients were randomly assigned to the exercise group or the control group using a computer program (<https://www.random.org>). Seven patients (three from the exercise group and four from the control group) did not complete the follow-up. The study flowchart is presented as shown in Figure 1. **Intervention**

During the study, the patients' pre-existing medical treatments were not altered. The exercise group was provided with a home-based exercise program. We did not prohibit the control group from exercising, although they did not receive any specific exercise recommendations. The home-based exercise program was instructed by the researcher physician in the PMR outpatient clinic, and a visual and descriptive brochure of the exercises was provided to the patients. The home-based exercise program, which included stretching and strengthening exercises, was followed at home for 12 weeks. The program consisted of stretching exercises targeting the neck, back, chest, and thigh muscles, as well as strengthening exercises focused on the back, shoulders, abdomen, and thigh muscles. The home-based exercise program was adapted from the Fibromyalgia Syndrome Patient Handbook, developed by the Turkish Society of Physical Medicine and Rehabilitation (available at: <https://www.tftr.org.tr/uploads/fibromiyalji-sendromu-hasta-kitapcigi.pdf>). Patients were advised to perform the exercises daily, if possible. If daily adherence was not feasible, they were recommended to exercise at least three days per week. To promote adherence in the exercise group, patients were contacted by phone every three weeks. During the final phone call, patients were invited to the outpatient clinic for their week 12 follow-up assessments. Patients in the control group were also contacted and invited for their evaluations at week 12.

## Outcome measures

The data were collected through face-to-face interviews with patients, using their self-reports. The patients' age, body mass index (BMI), smoking status, disease duration (in years), and exercise habits were recorded. The survey primarily encompassed demographic characteristics, pain severity, fatigue, depressive symptoms, exercise perception, and quality of life measures. All participants were required to complete the questionnaires at baseline and at the 12-week follow-up.

Pain and fatigue were evaluated using the VAS score, whose reliability was confirmed by Clark et al. [16]. This scale consists of a 10 cm horizontal line where "0" represents "no pain"

and "10" signifies "unbearable pain" for pain measurement, "0" indicates "no fatigue" and "10" represents "intolerable fatigue" for fatigue evaluation. Patients were instructed to indicate the severity of their pain and fatigue on the horizontal line. Quality of life was evaluated using the Turkish version of the Fibromyalgia Impact Questionnaire (FIQ) [17]. This tool consists of 10 subscales, each scored from 0 to 10, covering areas such as "physical impairment," "days feeling well," "missed work," "work-related impairment," "pain," "fatigue," "morning fatigue," "stiffness," "anxiety," and "depression." The total FIQ score can range from 0 to 100, with higher scores reflecting a greater impact of the condition on the patient's well-being [18].

The Exercise Benefits and Barriers Scale (EBBS) was used to assess patients' exercise perceptions. This scale consists of 44 items, and patients are asked to select the most appropriate option on a 4-point Likert scale. Items 4, 6, 9, 12, 14, 16, 19, 21, 24, 28, 33, 38, 40, and 42 represent perceived barriers to exercise, whereas the remaining items reflect perceived benefits. Scores for the benefits and barriers subscales are calculated separately. Higher scores on the benefits subscale indicate a more positive perception of exercise, while higher scores on the barriers subscale suggest a greater perception of obstacles to engaging in exercise. The Turkish validity and reliability study of this scale has been conducted [19].

Beck Depression Inventory (BDI) was used to assess the patients' depressive symptoms. The validity and reliability of the Turkish version of this scale have been established [20].

### **Statistical analysis**

Descriptive statistics of the data are presented as mean, standard deviation, median, minimum, maximum, frequency, and percentage values. The normality assumption of quantitative data was checked using the Shapiro-Wilk test. Differences between exercise and control groups in terms of demographic variables were analyzed. For variables showing normal distribution, the Independent Samples t-test was used, while the Mann-Whitney U test was used for variables that did not meet the normality assumption. Relationships between categorical variables were examined using the Pearson Chi-square test. For VAS, EBBS, BDI, and FIQ, the BrunnerLanger F1-LD-F1 model (One independent factor: Group. One dependent factor: Time) was used. After significant interaction, within-group and between-group comparisons were made. Differences between time points within each group were analyzed using the Brunner-Langer analysis with LD-F1 design. Mann-Whitney U test was used for between-group comparisons at each time point. Statistical analyses were performed using R software (R

Foundation for Statistical Computing, version 4.4.1, packages: nparLD, Vienna, Austria; <http://r-project.org>) and IBM SPSS Statistics 25.0 (IBM SPSS Statistics for Windows, Version 25.0. Armonk, NY: IBM Corp.). The significance level was set at 0.05 for all analyses, except for interactions, where  $p < 0.1$ .

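### The group-by-time interaction is the treatment-effect test but is judged at p<0.1 on about six scores, and the available sections do not say which test decides benefit

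*Combined protocol and SAP*

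**What the plan says.** All quotes in this field are from the combined document.

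- **Model (Statistical analysis).** "For VAS, EBBS, BDI, and FIQ, the BrunnerLanger F1-LD-F1 model", with the factors given as "One independent factor: Group. One dependent factor: Time".
- **Sequence (Statistical analysis).** "After significant interaction, within-group and between-group comparisons were made". Within each arm: "Differences between time points within each group were analyzed using the Brunner-Langer analysis with LD-F1 design". Between arms: "Mann-Whitney U test was used for between-group comparisons at each time point".
- **Thresholds (Statistical analysis, last sentence).** "The significance level was set at 0.05 for all analyses, except for interactions, where" the limit is p<0.1. This sentence is the one that needs to change.
- **Visits (Outcome measures).** "All participants were required to complete the questionnaires at baseline and at the 12-week follow-up".
- **Scores (Outcome measures).** The VAS is used once for pain and once for fatigue. For the EBBS, "Scores for the benefits and barriers subscales are calculated separately". The BDI and the FIQ total add one score each.

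The sections Study design and participants, Intervention, Outcome measures and Statistical analysis name no primary outcome, no ordering of outcomes and no multiplicity adjustment. The pages before them were not available for this review, so these absences are claimed for those four sections only.

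**The concern.** A looser threshold for interactions is common when screening for effect modification, where the treatment effect is tested elsewhere. Here it is not tested elsewhere: the interaction is the only test in the plan that compares change between the randomised arms. The key test therefore has the loosest threshold, and it is repeated over several scores without adjustment.

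A significant interaction then opens two kinds of follow-up at 0.05, and they protect a claim very differently. A between-arm difference at week 12 is a second randomised comparison. A change within the exercise arm is not: it also picks up any improvement that both arms share. Such improvement is plausible here, because entry required a pain score of at least 4 out of 10 (which invites regression to the mean) and the outcomes are self-reported. At stake is whether a reader can tell how strong the evidence behind a statement of benefit is.

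**Working it through.** **Inputs from the document.** Interaction threshold 0.1; other tests 0.05 (taken as two-sided); two visits; 60 women randomised; 3 exercise and 4 control patients lost to follow-up.

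**Assumptions.** Allocation 30/30 (the ratio is not stated), so 30 − 3 = 27 and 30 − 4 = 26 completers. Pre-post correlation r = 0.5. Equal correlation ρ between scores of 0.3, 0.5 or 0.7; some positive correlation is likely, since the FIQ itself contains pain, fatigue and depression components. FIQ subscales are not tested separately.

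**The plan's own figure.** The available sections give no power or error-rate calculation, so there is none to reproduce. The 0.1 is a stated threshold.

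**Step 1: what the interaction tests.** Rank all values of a score over both arms and visits, and let D be a patient's week-12 rank minus her baseline rank. With two visits the interaction test reduces to

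T = (mean D in exercise − mean D in control) / √(s²_E/n_E + s²_C/n_C).

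That is a between-arm comparison of change.

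**Step 2: number of scores.** VAS 2 + EBBS 2 + BDI 1 + FIQ 1 = 6. If one score per listed instrument is modelled, 4.

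**Step 3: nominal rates for independent scores, either direction.**

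- Six at 0.1: 1 − 0.9⁶ = 0.469. Four at 0.1: 1 − 0.9⁴ = 0.344.
- Six at 0.05: 1 − 0.95⁶ = 0.265.
- Six at 0.05/6 = 0.0083: 1 − (1 − 0.0083)⁶ = 0.049.

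**Step 4: correlated scores under no exercise effect.** The plan's rank tests were simulated on normal scores, 40,000 trials per setting, apart from the row marked †, which comes from a separate run of 8,000. Entries are the chance that at least one of six scores meets the rule.

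| Rule | ρ=0.3 | ρ=0.5 | ρ=0.7 |
|---|---|---|---|
| Interaction p<0.1, either direction | 45% | 40% | 33% |
| Interaction p<0.1, favouring exercise | 24% | 20% | 17% |
| Same, plus within-exercise improvement, no trend | 8% | 7% | 6% |
| Same, both arms improve 0.25 SD | 20% | 18% | 14% |
| Same, both arms improve 0.5 SD | 24% | 20% | 16% |
| Interaction p<0.1 plus week-12 Mann-Whitney, favouring exercise | 4.2% | 3.7% | 3.1% |
| Interaction p<0.05 unadjusted, favouring exercise | 14% | 12% | 10% |
| Holm at 0.05, either direction | 6.1% | 5.5% | 4.6% |
| Holm at 0.05, favouring exercise† | 2.1-3.1% over the range | | |

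For scale, one two-sided test at 0.05 favours exercise falsely with chance 0.05/2 = 2.5%.

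With four scores, the interaction favouring exercise gives 18% / 15% / 13%, and adding the week-12 test gives 2.9% / 2.7% / 2.3%. Varying r from 0.3 to 0.7 with six scores gives 16-24% for the interaction favouring exercise and 2.4-5.1% with the week-12 test added.

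**Step 5: power for one isolated effect (all d assumed, r = 0.5).**

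| d | Interaction at 0.10 | At 0.05 | First Holm step (0.0083) | Interaction at 0.10 plus week-12 test |
|---|---|---|---|---|
| 0.5 | 54% | 42% | 20% | 30% |
| 0.78 | 86% | 77% | 54% | 70% |
| 1.0 | 96% | 93% | 79% | 91% |

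**The case against.** The strongest reply is that the interaction is only a gate. On that view the 0.05 follow-up tests carry the claim, and the between-arm follow-up after treatment is the week-12 Mann-Whitney test. If both are required, the chance of a false result favouring exercise is about 3-4%. If within-exercise improvement is required as well, it is about 1.0-1.5% with no trend and 3-4% with a shared 0.5 SD gain. Against that reading the proposed change gains little. On the same favouring-exercise scale Holm gives about 2-3%, roughly one percentage point better. At d = 0.78 it costs 70% − 54% = 16 points of power for an isolated effect when r = 0.5. The cost is larger at r = 0.3 (65% against about 38%) and vanishes at r = 0.7 (76% against 78%).

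Much of this stands. A reader might infer that p<0.1 on six scores shows a false-positive rate of 40% or more, or that any benefit reported from this trial is spurious. The document supports neither inference. The 33-45% figures count either direction and let the interaction alone decide, and no sentence says that it does.

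The reply does not remove the concern, because no sentence says that the week-12 test decides either. Within-group and between-group comparisons are opened together, with equal standing.

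Two smaller objections also have weight. The six-score family mixes symptoms with exercise perceptions, which is a judgement; the four-score results show the same pattern. And a family and deciding test named after the data are in cannot confirm anything, which the recommended wording respects.

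**Conclusion.** The concern holds in limited form. The treatment-effect test is judged at twice the level used for every other test, over about six scores, and the available sections state no multiplicity control and no deciding test. The resulting chance of falsely favouring exercise is inflated under two of the three readings: 17-24% if the interaction alone suffices, and 6-8% (no trend) to 16-24% (0.5 SD gain in both arms) if within-exercise improvement is added. Under the third reading, interaction plus week-12 difference, it is about 3-4% and there is little to correct beyond stating the rule.

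These sizes rest on the assumed 27 v 26 split, correlations, normal scores and shared trends. What does not rest on them is that the text does not let a reader tell which reading applies.

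**What to change.** Revise the closing sentences of Statistical analysis, from the follow-up comparisons to the significance levels, so that they say the following:

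1. The group-by-time interaction is the deciding test for each score, judged at 0.05, the plan's own level elsewhere.
2. Within-group and time-point comparisons are descriptive, so a change within the exercise arm cannot support a claim of benefit.
3. Holm-adjusted p-values over the modelled scores (six, or four if only four are modelled) are reported beside the unadjusted ones. Moving to 0.05 without adjustment would still leave 10-14% favouring exercise.
4. The family and deciding test were set after data collection, so no benefit is called confirmed. Results with Holm-adjusted p<0.05 are described as better supported and the rest as exploratory. Familywise control is approximate, because the rank test uses a large-sample reference.

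The cost is one adjusted p-value per score and a rewritten rule, with no new data. The real price is power for an isolated effect. At an assumed d of 0.78 and r = 0.5 it falls from 86% at 0.10 to 77% at 0.05 and 54% at the first Holm step. Keeping the unadjusted p-values in view leaves weaker signals visible.

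### The formal week-12 comparison of the arms is made only after a significant interaction, so the outcomes that are formally compared are selected for significance (minor)

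*Combined protocol and SAP*

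**What the plan says.** All of the relevant analysis text is in the Statistical analysis section. For VAS, EBBS, BDI and FIQ the Brunner-Langer "F1-LD-F1 model (One independent factor: Group. One dependent factor: Time) was used". The next sentence sets the condition: "After significant interaction, within-group and between-group comparisons were made". The text then names the tests for those follow-up comparisons: an LD-F1 analysis within each arm, and between arms "Mann-Whitney U test was used for between-group comparisons at each time point". On thresholds, "The significance level was set at 0.05 for all analyses, except for interactions", which are judged at p < 0.1.

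There are two visits (Outcome measures): "All participants were required to complete the questionnaires at baseline and at the 12-week follow-up". Pain and fatigue each have a VAS, and for the EBBS "Scores for the benefits and barriers subscales are calculated separately". With FIQ and BDI that makes six scores.

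The Statistical analysis section also says that descriptive statistics are presented, without linking them to the interaction result. It specifies no estimate of the arm difference and no confidence interval for any outcome.

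**The concern.** In a randomised trial with two arms and one follow-up visit, the arm difference at week 12 is the direct answer to the trial's question, and it should be given for every outcome. Here the formal comparison depends on a preliminary test of the same data. The sentence on the Mann-Whitney test follows the condition and describes how the conditional comparisons are made, so the natural reading is that no ungated comparison exists.

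The interaction and the week-12 difference are positively correlated, because both rise when the exercise arm happens to do well at week 12. Choosing outcomes by the first therefore favours those where the second is large by chance. A reader who looks only at the outcomes formally compared would see a benefit that is, on average, overstated. The outcomes that missed the gate would have no matching result to set against it.

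**Working it through.** The documents contain no power calculation, expected effect or sample-size figure, so there is none to reproduce. The gate was simulated instead.

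**Inputs from the documents**
- Study design and participants: "A total of 60 female patients" took part, and "Seven patients (three from the exercise group and four from the control group) did not complete the follow-up". Completers: 60 − 7 = 53.
- Statistical analysis: gate at interaction p < 0.1; Mann-Whitney at 0.05.
- Outcome measures: two visits.

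**Assumptions**
- Equal allocation, which is not stated: 30 − 3 = 27 exercise and 30 − 4 = 26 control.
- Two-sided tests; normally distributed scores with SD 1.
- Baseline to week-12 correlation r = 0.3, 0.5 or 0.7.
- True effect d = 0.3, 0.5 or 0.8 SD at week 12.

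**Method** (20,000 trials per scenario)
1. Rank all observations together. For each patient take c = rank at week 12 − rank at baseline.
2. Interaction statistic: z = (mean c, exercise − mean c, control) / √(s₁²/27 + s₂²/26). This approximates the F1-LD-F1 interaction test. The gate passes if two-sided p < 0.10.
3. Week-12 test: Mann-Whitney U, normal approximation, two-sided 0.05.
4. Record the share failing the gate and the mean week-12 difference among those passing. Inflation = passing mean / d − 1.

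| d | r | gate fails | mean difference if passed | inflation |
|---|---|---|---|---|
| 0.3 | 0.3 | 76.2% | 0.481 | 60% |
| 0.3 | 0.5 | 71.1% | 0.447 | 49% |
| 0.3 | 0.7 | 62.1% | 0.400 | 33% |
| 0.5 | 0.3 | 56.0% | 0.635 | 27% |
| 0.5 | 0.5 | 45.4% | 0.595 | 19% |
| 0.5 | 0.7 | 28.6% | 0.550 | 10% |
| 0.8 | 0.3 | 23.7% | 0.860 | 8% |
| 0.8 | 0.5 | 12.9% | 0.832 | 4% |
| 0.8 | 0.7 | 3.3% | 0.805 | 1% |

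Example: at d = 0.5 and r = 0.5, 0.595/0.5 − 1 = 19%. Repeat runs under the same assumptions move these figures by about one percentage point; at 0.5 SD they span 28–56% failing and 9–28% inflation. Averaged over all trials, without the gate, the mean difference equals the true effect (0.30, 0.50 and 0.80 SD).

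**What the gate withholds.** At d = 0.5 and r = 0.5 the week-12 Mann-Whitney test is significant in 41.0% of trials and both tests are significant in 30.4%. So in 41.0 − 30.4 = 10.6% of trials a significant week-12 result would never be computed. In a run of 6,000 trials, those cases had a mean week-12 difference of 0.70 SD, but the exercise arm was already ahead at baseline by a mean of 0.37 SD. About half of that difference (0.37/0.70 = 53%) was present before any exercise. This bears on the fix: an unadjusted week-12 test would count that imbalance as benefit.

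**The case against.** The strongest reply is that little is lost, and much of it stands.

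- **Every outcome is tested between arms.** With two visits, Group by Time is a between-arm test of change, and it is run for every outcome. A reader might infer that an outcome failing the gate has no test of exercise, or only the Group and Time main effects. The documents do not support that, and they nowhere present those main effects as evidence of benefit.
- **Descriptive statistics are not gated.** A reader might infer that weak outcomes vanish or cannot be recovered for a meta-analysis. The text gives no ground for this. It does not spell out that summaries are by arm and visit, but nothing says they are withheld.
- **The gate is not harsh compared with the test it precedes.** At d = 0.5 and r = 0.5 it passes 54.6% of trials, against 41.0% for the week-12 Mann-Whitney test.
- **Not all inflation comes from the gate.** Where both tests are significant at d = 0.5 the mean difference is 0.77 SD. That might be held against the gate, but it is 0.75 SD among trials with a significant Mann-Whitney test and no gate. Nearly all of it is the ordinary effect of selecting on significance.
- **The plan computes no effect estimate at the gated step.** The inflation therefore describes the differences underlying the comparisons made, not a statistic the plan names.
- **Testing the interaction first is conventional and limits further testing.** True, but as error control it is weak: with six independent null outcomes the chance that at least one passes is 1 − 0.9⁶ = 46.9%.

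None of this removes the selection. An interaction p-value from a rank model gives no size or precision in the units of the score, so it does not replace a reported week-12 difference.

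**Conclusion.** The point holds as a minor one about reporting. The formal week-12 comparison depends on the interaction reaching p < 0.1, so the outcomes formally compared are selected for significance. The resulting bias is substantial if true effects are small (about 33–60% at 0.3 SD), moderate at 0.5 SD (about 9–28%) and negligible to small at 0.8 SD (about 1–8%).

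These sizes rest on assumed effects, correlations, equal allocation, normal scores and two-sided testing; none of these is given in the documents. The direction was the same in every scenario. The conclusion also rests on reading the condition as exclusive, which is the natural reading of the text.

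**What to change.** In the Statistical analysis section, remove the significant interaction as a condition for the between-arm comparison. For all six scores (pain VAS, fatigue VAS, FIQ, BDI, EBBS benefits, EBBS barriers), report the week-12 arm difference adjusted for the baseline score, with a 95% confidence interval. Give the interaction p-value beside it, whatever its value. Adjustment matters because of the baseline imbalance shown above; simply adding six unadjusted Mann-Whitney p-values would not be a clear improvement.

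The cost is a change of wording and a few extra table rows from data already collected. Some reported effects will look smaller.

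### No between-group estimate with a confidence interval, and no analysis that conditions on the baseline score; the week-12 comparison is an unadjusted test made only after a significant interaction

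*Combined protocol and SAP*

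**What the plan says.** The scores were collected twice (Outcome measures): "All participants were required to complete the questionnaires at baseline and at the 12-week follow-up". The Statistical analysis section then sets out the following steps.

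- Main model: "For VAS, EBBS, BDI, and FIQ, the BrunnerLanger F1-LD-F1 model (One independent factor: Group. One dependent factor: Time) was used". Baseline enters as the first level of Time, that is, as an outcome. No covariate is named.
- Gate: "After significant interaction, within-group and between-group comparisons were made". The threshold for interactions is p < 0.1; elsewhere it is 0.05.
- Between-group step: "Mann-Whitney U test was used for between-group comparisons at each time point".
- Within-group step: "Differences between time points within each group were analyzed using the Brunner-Langer analysis with LD-F1 design".
- Summaries: "Descriptive statistics of the data are presented as mean, standard deviation, median, minimum, maximum, frequency, and percentage values". No between-group effect measure and no confidence interval is described.

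On numbers, Study design and participants gives 60 randomised patients and adds: "Seven patients (three from the exercise group and four from the control group) did not complete the follow-up".

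**The concern.** The randomised question is how far week-12 scores differ between arms among patients who started alike. The interaction is a valid test of a treatment effect. With two time points, however, it is in effect a comparison of rank changes, which uses baseline without conditioning on it. The Mann-Whitney test at week 12 ignores baseline, and the Mann-Whitney test at baseline examines a null that randomisation already makes true. The within-group tests do not compare treatments.

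Two things are at stake. One is precision: only 53 of the 60 patients are evaluable, and a strong predictor of the week-12 score is not used as such. The other is interpretation. If the interaction is not significant, the plan stops, and nothing it describes tells the reader which effects the trial has excluded. If it is significant, the week-12 differences then examined are a selected set and run large when the true effect is modest.

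**Working it through.** **Inputs from the documents.** 60 randomised; 3 (exercise) and 4 (control) lost, so 60 − 7 = 53 with follow-up; thresholds 0.05, and 0.1 for interactions. The plan gives no power, effect size or SD, so there is no figure of its own to reproduce.

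**Assumptions.** 30 per arm, hence 27 and 26 completers; r = 0.3, 0.5 or 0.7; two-sided tests; unit SD.

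**Analytic check.** The variance of the group difference, relative to an unadjusted week-12 comparison of means, is 1 for week 12 alone, 2(1 − r) for change and 1 − r² for ANCOVA. With √(1/27 + 1/26) = 0.2748, the unadjusted 95% half-width is 1.96 × 0.2748 = 0.54 SD and the difference detectable with 80% power is (1.96 + 0.84) × 0.2748 = 0.77 SD. Multiplying by √(1 − r²) gives the ANCOVA rows.

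| | r = 0.3 | r = 0.5 | r = 0.7 |
|---|---|---|---|
| Variance factor, change | 1.40 | 1.00 | 0.60 |
| Variance factor, ANCOVA | 0.91 | 0.75 | 0.51 |
| Half-width, ANCOVA (SD) | 0.51 | 0.47 | 0.39 |
| Detectable difference, ANCOVA (SD) | 0.73 | 0.67 | 0.55 |
| Patients for an unadjusted week-12 comparison to match ANCOVA with 53: 53/(1 − r²) | 58 | 71 | 104 |
| The same for change: 53 × 2(1 − r)/(1 − r²) | 82 | 71 | 62 |

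**Simulation, normal scores, true effect 0.7 SD.** There were 12,000 runs per setting, except the HC3 row (5,000) and the rows given as ranges (separate simulations of 2,000 to 4,000 runs). The interaction is represented by a Welch test on the change in joint ranks, as a stand-in for F1-LD-F1.

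| Power, % | r = 0.3 | r = 0.5 | r = 0.7 |
|---|---|---|---|
| Mann-Whitney at week 12, ungated, 0.05 | 68 | 68 | 68 |
| Interaction at 0.05 | 54 | 66 | 85 |
| Interaction at the plan's 0.1 | 65–67 | 76–78 | 91–92 |
| Plan's sequence: interaction < 0.1, then Mann-Whitney < 0.05 | 52–56 | 57–60 | 64 |
| ANCOVA at 0.05 | 74 | 82 | 93 |
| ANCOVA with HC3 standard error, 0.05 | 71 | 80 | 92 |

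With no effect, the three tests at 0.05 reject in 4.5–4.9% of runs, so the differences are in efficiency, not validity. Simulated mean half-widths, which use t quantiles, are 0.55/0.55/0.55 SD unadjusted, 0.65/0.55/0.43 for change and 0.53/0.48/0.40 for ANCOVA.

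**The gate.** With a true effect of 0.3 SD, the interaction passes p < 0.1 in 23/27/37% of runs, so no follow-up comparison is made in 77/73/63%. Among runs that pass, the week-12 difference averages 0.48/0.45/0.40 SD instead of 0.3.

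**Skewed scores** (gamma, shape 2, pure shift of 0.7 SD; 5,000 runs). Power is 71/79/91% for HC3-ANCOVA, 81/83/82% for Mann-Whitney and 68/80/94% for the interaction. HC3 coverage is 96% here and 95–96% over all settings.

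**The case against.** The strongest reply is that two points of unequal weight are joined here. The missing estimate is a reporting gap; ANCOVA is a preference among valid tests. The efficiency gain depends on distribution: the scores are bounded, entry requires pain VAS of at least 4, and the plan chose rank methods. Under strong skew, Mann-Whitney has more power than HC3-ANCOVA at r = 0.3 and 0.5, and the interaction has slightly more at r = 0.5 and 0.7. That stands, so power cannot be the sole argument.

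Second, the plan's interaction threshold is 0.1, not 0.05. That is so, and at 0.1 its power at r = 0.7 is about that of HC3-ANCOVA at 0.05. It buys this with a false-positive rate of about 10%; at 0.10, ANCOVA reaches 83/89/97%.

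Third, the gate matters less for large effects. At 0.7 SD it passes in 65/77/92% of runs and the selected difference averages 0.78/0.75/0.71 SD. Selecting ANCOVA estimates on significance would inflate them too (0.66/0.61/0.52 SD at a true 0.3 SD, selected at p < 0.05). The cure for this part is to report regardless of the p-value, not to adjust for baseline.

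Fourth, arm means and SDs let a reader build an unadjusted week-12 interval. They do, so the effect size is not wholly hidden. They do not give the adjusted interval, which needs the within-patient correlation, and at r = 0.3 that interval is only slightly narrower.

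**Conclusion.** The concern holds. The plan describes no baseline-adjusted comparison and no between-group estimate with an interval, and makes its direct comparison of arms only after a significant interaction. The estimation gap does not depend on distribution. The efficiency loss does: for roughly normal scores, adjustment narrows the unadjusted week-12 interval by about 4%, 13% or 27% (0.53, 0.48 or 0.40 against 0.55 SD) at r = 0.3, 0.5 or 0.7; under strong skew there is no consistent power gain. These sizes rest on assumed equal allocation and assumed correlations. The planned tests remain valid, so this should be fixed but does not invalidate the analysis.

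**What to change.** For each of the six scores (pain VAS, fatigue VAS, EBBS benefits, EBBS barriers, BDI and FIQ total), report the week-12 exercise-minus-control difference from a linear ANCOVA with that score's baseline value as covariate and an HC3 robust 95% CI. Do this whatever the interaction p-value, and use this one method throughout, without choosing it from the residuals.

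Keep the F1-LD-F1 interaction beside it as the analysis originally described. Drop the baseline Mann-Whitney test, and show within-group changes descriptively, not as evidence of a treatment effect. State that the estimates rest on patients with a week-12 score; handling of the seven without one is a separate question that this change does not settle. Because the document describes the trial as already conducted, label the added analysis post hoc.

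The cost is a few lines of R per outcome, one results column and one sentence. No new data are needed.
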